7.7 Secondary Endpoints

Secondary endpoints include:

- All cause death
- Hospitalization for nonfatal MI
- Hospitalization for nonfatal stroke
- Coronary revascularization (PCI or CABG)
- Quality of life and functional status components include:
 - o Current Health
 - Physical function
 - Depression
 - Fatigue
 - Sleep disturbance
 - Social roles and activities
 - Pain Interference

Patient reported coronary revascularization events that do not match to one of the electronic sources will not be further verified. As such, these PROs will not be counted as events in the secondary event analyses.

All-cause death will be analyzed using a Cox proportional hazards model. All other time-to-event outcomes will be analyzed using the Fine and Gray method, equivalent to the Cox proportional-hazards model when competing risks are present, with all-cause death as the competing risk. The test will be two-tailed and will be performed at an overall α of 0.05. The proportional hazards assumption will be checked for randomized treatment arm using weighted Schoenfeld residuals. If there is evidence of non-proportionality, a cautious interpretation of the model hazard ratio will be encouraged, and non-parametric event rate estimates will be emphasized, as described for the primary effectiveness analysis.

Quality of life and functional status data are collected on numerical scales (1:excellent health-5:worst health). They will be analyzed as continuous variables. Mixed models using restricted maximum likelihood estimation (REML) will be employed to model trajectory of measures over time by treatment group. Mixed models account for the correlation structure imposed by repeated measures within participants while using all available data, from baseline to the end of the study, regardless of exact follow-up time. The intercept and slope will be modeled as random effects. The covariance structure for random effects will be modeled using an unstructured form. Time from baseline measurement and randomized treatment arm will be included in the model as fixed effect. Time will be tested for linearity using natural cubic splines. An interaction between randomized treatment arm and time will be assessed, as will the overall effect of randomized treatment arm.

Since these measures are discrete scores, it is expected that normality assumptions will not hold. Natural log and other appropriate transformations will be considered, as well as several distributions and link functions.

No formal adjustments for multiple testing will be performed. All main and sensitivity analysis results will be presented and left to the interpretation of the reader.

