Data will be transferred from the sites to the DCRI using PopMedNet. The DCRI will be responsible for maintaining the confidentiality and security of transferred data. The control of access to databases will be managed centrally by the Duke Health Technology Solutions (DHTS) through user passwords linked to appropriate access privileges. This protects data from unauthorized view and modifications as well as inadvertent loss or damage. Duke has an extensive data security infrastructure. Database servers are secured by a firewall as well as through controlled physical access. Oracle has many security protection features that ensure that each person accessing the database has the proper authority to perform the functions he or she requests of the data management system. Within the secondary SAS datasets, UNIX

group access control will be used for maintaining similar security. The Sun workstation log-in will be secured by extensive user password facilities under UNIX.

III.E. Endpoints and Adverse Events

III.E.1. Primary Endpoint

The primary effectiveness analysis will be performed on the entire randomized (ITT) population. The primary endpoint of this study is the composite rate of all-cause mortality, hospitalization for nonfatal MI, or hospitalization for nonfatal stroke. Traditional reporting of potential endpoints by study sites with independent adjudication by a Clinical Events Committee will not be done in this trial given the pragmatic nature of the ADAPTABLE study and the low-cost trial budget. We are planning to implement an endpoint validation plan to ensure the accuracy of endpoint classification compared with clinical endpoint adjudication processes used in traditional clinical trials. Once approved, the description of the validation plan will be provided in a separate document. Validated coding algorithms will be applied to a variety of EHR data sources to comprehensively ascertain potential endpoints related to hospitalizations for the nonfatal component primary endpoints (MI and stroke) and the secondary endpoints. A recently published study demonstrated that events ascertainment and classification using coding algorithms with administrative claims data yielded similar results compared with the standard adjudication of events done in traditional clinical trials. The informed consent form will cover access to the data needed to support the validation plan.

III.E.2. Secondary Endpoints

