Secondary endpoints include the components of the primary endpoint, coronary revascularization procedures (PCI and CABG), and quality of life and functional status.

III.E.3. Safety Endpoints

[figure not shown]
The major safety endpoint is hospitalization for major bleeding with an associated blood product transfusion.

III.E.4. Identifying Endpoints

Endpoints will be ascertained by applying algorithms designed to ensure comprehensive surveillance for all potential endpoints. To supplement the PCORnet CDM data, Medicare data and health plan data will be obtained at regular intervals during the course of the study, for a portion of the study participants. Further details on the process and authorizations for Medicare and health plan data linkages are contained in a separate Linkage Plan document.

Routine queries will be applied to the PCORnet CDM, Medicare data, and health plan data to capture and classify nonfatal endpoints (hospitalization for MI, hospitalization for stroke, or hospitalization for major bleeding) using validated coding algorithms that will be applied to hospitalizations for each randomized participant. Because these electronic health data sources are the source of truth for the trial, no patient confirmation or other additional confirmation will be required for hospitalizations verified by the coding algorithms applied to these data sources (see figure below). Medicare data and health plan data are being queried to help identify endpoints that occur outside of the recruiting sites ("out-of-network" endpoints). Because we do not expect these other data sources to fully capture all out-of-network endpoints, we are

- also asking patients to report all hospitalizations that occur during the follow-up period via the ADAPTABLE participant web portal.

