- Medical record data for hospitalizations reported by participant on the ADAPTABLE participant web portal, but not captured by queries applied to the PCORnet CDM, Medicare data, or health plan data, will be obtained by the DCRI Call Center and used to classify the specified participant-reported hospitalizations using the same endpoint coding algorithms that will be applied to the EHR data sources (PCORnet CDM, Medicare data, and health plan data—see figure below. The role of the DCRI Call Center will be especially important for the final months of the follow-up period when, due to inherent data latency associated with these data sources, Medicare data and health plan data will not yet be available for confirming out-of-network hospitalizations reported on the ADAPTABLE participant web portal. Participant-reported hospitalizations that cannot be classified by applying coding algorithms will be clinically reviewed using available medical record data obtained by the DCRI Call Center and confirmed events will be included as trial endpoints.
- Deaths occurring in-hospital at participating network hospitals will be captured with CDM queries, but deaths are often not well represented in EHR data sources, especially out-ofhospital deaths, that are expected to be the majority of the accrued death events during the trial. Medicare data do include information about death events regardless of the location of death, but only for patients enrolled in and eligible for Medicare (Medicare gathers this information from claims, reports from family members, and benefit information collected from the Social Security Administration). The DCRI Call Center will often identify death events from participant-designated alternative contacts during ascertainment of vital status when 2 or more consecutive visits are not completed in the ADAPTABLE participant web portal and/or when final contact with the participant cannot be confirmed. Additionally, the DCRI Call Center will confirm and enter death information in cases where sites notify the study team of out-of-hospital deaths. A participant-locator service may be used during the course of the study to find participants who may have been lost to follow-up. This service will be used to ensure that contact at the end of the trial is made with as many participant as possible who do not complete their final visit to the web portal or complete their final visit via telephone contact with the DCRI Call Center.

III.E.4.a. Death

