This endpoint includes death from any cause (all-cause mortality).

III.E.4.b. Hospitalization for Nonfatal MI

The endpoint of hospitalization for nonfatal MI will be ascertained using ICD-10-CM diagnosis codes (to be listed in the SAP) associated with an encounter in a hospital setting. Priority will be given to diagnosis codes in the principal or primary position. Diagnosis codes in secondary or unknown positions also will be searched for the identification of potential endpoints. The extent to which events identified by diagnosis codes in secondary or unknown positions will or will not be used in the final analysis will be detailed in the SAP. The MI coding algorithm that will guide these efforts was validated for use in FDA's Mini-Sentinel program⁹² and has been shown to have a positive predictive value (PPV) of 86%. 93

III.E.4.c Hospitalization for Stroke

The endpoints of hospitalization for hemorrhagic stroke or ischemic stroke will be ascertained using ICD-10-CM diagnosis codes (to be listed in the SAP) associated with an encounter in a hospital setting. Priority will be given to diagnosis codes in the principal or primary position. Diagnosis codes in secondary or unknown positions also will be searched for the identification of potential endpoints. The extent to which events identified by diagnosis codes in secondary or unknown positions will or will not be used in the final analysis will be detailed in the SAP. The stroke coding algorithm that will guide these efforts has been shown to have a PPV 85% or greater. Is chemic stroke hospitalizations and hemorrhagic stroke hospitalizations will be incorporated into a combined endpoint of all stroke events.

III.E.4.d. Coronary Revascularization

Coronary revascularization includes all coronary revascularization procedures (PCI/CABG) performed during the study. These will be identified using ICD-10-PCS procedure codes and CPT procedure codes (to be listed in the SAP).

III.E.4.e. Hospitalization for Major Bleeding

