5.2 Secondary Endpoints

[figure not shown]
Secondary endpoints include the components of the primary endpoint, coronary revascularization procedures (PCI and CABG), and quality of life and functional status.

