7.5 Censoring Rules

In the event that a patient does not experience an efficacy or safety endpoint, the patient will be censored at the earliest of study end date or maximum follow-up time point at which the patient can be reasonably assumed to be event free. The maximum follow-up time point will be determined from any of the following data sources: CDM censor date, CMS censor date, private health insurance censor date, or the web portal censor date (last point of contact).We expect the study end date to occur on or before all follow-up time points; however, for completeness, censoring dates are defined below. Patients who withdraw consent for trial follow-up will be censored at the time consent is withdrawn. Patients who consent to limited participation follow-up will be censored at the earliest follow-up time point as delineated.

The censoring date for CDM data will be at the site-specific censoring date, which is determined by the PCORnet Distributed Research Network Operations Center based on data curation query results. The censoring date for CMS will be the minimum of the end of enrollment in fee-forservice or the last date claims data are available. The censoring date for private health insurance claims will be the minimum of the end of claims enrollment or the last date claims data are available.

Time to event modeling will include the first occurrence of an event where the time to event is calculated as the event date – randomization date +1.

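### SAP 7.7 drops self-reported PCI or CABG that has no electronic match without checking it, although the protocol already retrieves records for such admissions; this secondary endpoint will be under-counted

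*SAP*

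**What the plan says.** Coronary revascularization is a named secondary endpoint. SAP 5.2 says: "Secondary endpoints include the components of the primary endpoint, coronary revascularization procedures (PCI and CABG), and quality of life and functional status". Protocol III.E.4.d defines it without any limit to in-network care: "Coronary revascularization includes all coronary revascularization procedures (PCI/CABG) performed during the study".

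SAP 7.7 then sets a rule for this endpoint alone: "Patient reported coronary revascularization events that do not match to one of the electronic sources will not be further verified". The next sentence gives the consequence: "As such, these PROs will not be counted as events in the secondary event analyses". No reason is given.

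Protocol III.E.4 explains why participants are asked to report hospitalizations at all. Of Medicare and health plan data it says: "Because we do not expect these other data sources to fully capture all out-of-network endpoints". For a reported hospitalization that the electronic queries did not find, the medical record data "will be obtained by the DCRI Call Center and used to classify the specified participant-reported hospitalizations using the same endpoint coding algorithms" that are used for the electronic sources. Admissions that the algorithms cannot classify go to clinical review, and events confirmed that way count as endpoints.

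SAP 6 refers to the protocol for endpoint identification and reports that some patient-reported endpoints were confirmed from medical records. SAP 7.9.2 names the portal with confirmation of reported events among the sources for both primary and secondary event-free survival analyses. Under SAP 7.5, a participant with no counted event is followed to the earlier of study end and the "maximum follow-up time point at which the patient can be reasonably assumed to be event free".

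**The concern.** The rule in SAP 7.7 is narrower than the endpoint it serves. SAP 6 lists the electronic sources as the CDM, CMS claims and private claims. A hospital record obtained by the Call Center is not among them, so a procedure documented only in such a record does not meet the matching condition.

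Take a participant admitted out of network with an MI and treated by PCI, with no claims linkage. The participant reports the admission and the record is retrieved. The MI can be confirmed from it and counted. On the literal reading of SAP 7.7, the PCI in the same record is not counted, and the participant stays in the revascularization risk set as event-free.

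At stake are the completeness of a named secondary endpoint and the accuracy of its reported event rates. The loss should be greatest among participants without claims linkage. It should also be greater in the final months, when protocol III.E.4 says Medicare and health plan data will not yet be available.

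**Working it through.** The documents give no event count, rate or power for revascularization, so there is no stated figure to reproduce. The main check is textual. The arithmetic only shows what a loss of a given size would do.

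**Passages side by side**

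| Question | Rest of the plan | SAP 7.7 |
|---|---|---|
| Which procedures are in the endpoint? | All PCI/CABG during the study (protocol III.E.4.d) | Only those with an electronic match |
| What happens to a reported admission not found electronically? | Record obtained and classified; confirmed events count (protocol III.E.4) | Revascularization not verified, not counted |
| Is the portal with confirmation a source for secondary analyses? | Yes (SAP 7.9.2) | Not for revascularization |
| Is the record-confirmed route reliable? | Near-perfect specificity assumed (SAP 7.10) | Route not used |

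The under-reporting analyses in SAP 7.10 are planned for the primary endpoints. Extending them to key secondary endpoints is optional, so no planned analysis is bound to show the effect of this rule.

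**Effect of losing a share f of events (f is assumed)**

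*Precision.* With 1:1 allocation, SE(log HR) ≈ 2/√D for D events. Losing a share f multiplies it by 1/√(1 − f):
- f = 0.10: 1/√0.90 = 1.05
- f = 0.20: 1/√0.80 = 1.12
- f = 0.30: 1/√0.70 = 1.20

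*Absolute rates.* Assume 3% per year in one arm, a true hazard ratio of 0.85, 50 months of follow-up, exponential times, no competing deaths, and the same loss in both arms.
- True incidence: 1 − exp(−0.03 × 50/12) = 11.75%, and 1 − exp(−0.85 × 0.03 × 50/12) = 10.08%. The difference is 1.67 points.
- With f = 0.20: 0.80 × 11.75% = 9.40%, and 0.80 × 10.08% = 8.06%. The difference is 1.34 points.

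*Hazard ratio, equal loss.* The observed ratio is approximately ln(1 − 0.0806)/ln(1 − 0.0940) = 0.852, against a true 0.85. Across assumed rates of 2% to 5% per year it is 0.8506 to 0.8515 with 10% lost, and 0.8516 to 0.8543 with 30% lost.

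*Hazard ratio, unequal loss.* With no true effect, capture of 90% in one arm and 95% in the other gives about 0.90/0.95 = 0.95. Capture of 80% and 90% gives about 0.80/0.90 = 0.89. Nothing in the documents shows that capture differs by arm.

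**The case against.** The rule is stated openly, and the SAP synopsis warns of some differences from the protocol. Requiring an electronic match favours specificity, which is defensible for a comparison of arms, especially in an open-label trial. With equal loss the hazard ratio is nearly unaffected. SAP 7.10 states non-differential error as an assumption for the primary and related secondary analyses. These arguments stand, and they limit how much the rule matters. The synopsis warning, however, concerns statistical methodology. This is ascertainment, for which SAP 6 points back to the protocol.

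Four stronger readings are tempting, and the documents do not support them.

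- *That the protocol expressly promises record review for revascularization.* Protocol III.E.1 speaks of algorithms that "comprehensively ascertain potential endpoints related to hospitalizations for the nonfatal component primary endpoints (MI and stroke) and the secondary endpoints", but that sentence concerns algorithms run on EHR data sources. The query list in III.E.4 names only MI, stroke and major bleeding. The retrieval text covers reported hospitalizations generally and does not name revascularization. The conflict therefore rests on the endpoint definition, the general retrieval text and SAP 7.9.2 taken together.
- *That the SAP says outright that a PCI in a retrieved record is thrown away.* That is the literal consequence of SAP 7.7, but the case is not spelled out. The Query Technical Specifications, to which SAP 6 refers for detail, are not among the documents.
- *That portal dates inflate follow-up and need their own censoring rule here.* SAP 7.5 expects study end to come no later than the source-specific dates, so the portal date should seldom decide censoring. The CDM date is set by site. A participant treated out of network stays at risk to that date with or without the portal.
- *That the fix would recover the whole 10% to 30%.* Unreported procedures, procedures without an admission, and events in participants who did not consent to confirmation stay uncaptured. A later matched procedure still counts, so some first events are delayed and not lost.

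**Conclusion.** The inconsistency is real and should be resolved. As written, SAP 7.7 leaves out revascularizations that could be confirmed from records the trial already obtains, and keeps those participants at risk as event-free. Cumulative incidence and absolute difference shrink in proportion to the loss. The standard error grows by a factor of 1.05 to 1.20 if 10% to 30% of events are lost. That range is an assumption, and it is an upper bound on what the fix can recover.

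A reader might infer that the treatment comparison is biased. The documents do not support that: with equal loss by arm the hazard ratio is essentially unchanged. Equal loss is itself an assumption in an open-label trial, and tabulating unmatched reports by arm would help to examine it. The point concerns one secondary endpoint. The primary effectiveness and primary safety analyses are not affected.

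**What to change.** Replace the two sentences in SAP 7.7 with three commitments:

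1. The PCI/CABG definitions are applied to medical records already obtained under protocol III.E.4, and procedures found there count as events on the procedure date.
2. Self-reported revascularizations that remain unmatched are tabulated by arm.
3. One sensitivity analysis counts those remaining reports as events.

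No separate portal-date censoring rule is needed.

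The cost is the SAP wording and some additional abstraction from records already held. SAP version 1.2 is dated February 9, 2021, and describes record confirmation in the past tense, so this may mean going back to records already processed. Counting unverified reports can add false positives, but only in the sensitivity analysis.

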The endpoints of hospitalization for intracranial bleeding, GI bleeding, and bleeding at another location will be ascertained using ICD-10-CM diagnosis codes (to be listed in the SAP) in a hospital setting. Priority will be given to diagnosis codes in the principal or primary position. Diagnosis codes in secondary or unknown positions also will be searched for the identification of potential endpoints. The extent to which events identified by diagnosis codes in secondary or unknown positions will or will not be used in the final analysis will be detailed in the SAP. The bleeding coding algorithm that will guide these efforts has been shown to have a PPV of 92%. Additionally, procedure codes will be searched for control of bleeding and blood product transfusions and may be used in combination with the diagnosis codes for the definition of the composite major bleeding outcome.

III.E.4.f. Quality of Life and Functional Status

In addition to the effectiveness and safety endpoints listed above, we will collect data on quality of life and functional status as shown in **Table 5**:

Table 5. PCORI Pat	ient-Reported Outcomes Common Measures -	– Core and Recommended (LOINC Panel 75418-4)
Domain	Item text	Answer list
General Health	In general, would you say your health is	5=Excellent; 4=Very good; 3=Good; 2=Fair; 1=Poor
Quality of life	In general, would you say your quality of life is	5=Excellent; 4=Very good; 3=Good; 2=Fair; 1=Poor
Physical Function	Are you able to run errands and shop?	5=Without any difficulty; 4=With a little difficulty; 3=With some difficulty; 2=With much difficulty; 1=Unable to do
Depression	In the past 7 daysI felt depressed	1=Never; 2=Rarely; 3=Sometimes; 4=Often; 5=Always
Fatigue	During the past 7 daysI feel fatigued	1=Not at all; 2=A little bit; 3=Somewhat; 4=Quite a bit; 5=Very much
Sleep Disturbance	In the past 7 daysI had a problem with my sleep	1=Not at all; 2=A little bit; 3=Somewhat; 4=Quite a bit; 5=Very much
Social Roles & Activities	I have trouble doing all of my regular leisure activities with others	5=Never; 4=Rarely; 3=Sometimes; 2=Usually; 1=Always

III.E.5. Events Collection

(Refer to Section III.A.5.d. Identifying Endpoints.)

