Assuming an annualized event rate of 4.6% in the higher risk arm and a 15% RR reduction (annualized event rate 3.8% in the lower risk arm) leads to 88% power and requires 1322 primary outcome events.

For the primary safety endpoint of hospitalization for major bleeding, power calculations were based on

Table 6					
Overall annualized event rate (%)	Relative Risk	Annualized event rate in low risk group (%)	Annualized event rate in high risk group (%)	Number of Events	Power
4.2	0.800	3.7	4.7	1321	0.99
4.2	0.825	3.8	4.6	1320	0.96
4.2	0.850	3.9	4.5	1322	0.88
4.4	0.800	3.9	4.9	1381	0.99
4.4	0.825	4.0	4.8	1381	0.97
4.4	0.850	4.1	4.8	1383	0.89
4.6	0.800	4.1	5.1	1441	0.99
4.6	0.825	4.2	5.0	1442	0.97
4.6	0.850	4.2	5.0	1439	0.90
4.8	0.800	4.3	5.3	1501	1.00
4.8	0.825	4.3	5.3	1502	0.98
4.8	0.850	4.4	5.2	1503	0.92

estimated primary event rates of 2%, 2.5%, and 3% per year (in the higher dose arm); annualized rate of loss to follow-up of 5%; 2-sided significance level alpha of 0.05; 7,500 participants in each treatment arm; total enrollment of 38 months; and a maximum follow-up period of 50 months. The power of the chosen testing strategy to detect a statistically significant difference in hospitalization for bleeding under these assumptions is shown in **Table 7**. Under all event rate scenarios, there will be power greater than 85% to detect an RR reduction of 25%, and for event rates of 2.5% or greater, power will be close to 80% to detect an RR reduction of 20%.

III.F.6. Secondary Endpoints

Secondary endpoints include the components of the primary endpoint, coronary revascularization procedures, quality of life, and functional status (Section III.A.5.a). Time-to-event outcomes will be analyzed using the same approach as the one used for the primary endpoint. Variables collected on numerical scales will be analyzed as continuous variables. Linear repeated measures mixed model will be employed to compare the 2 treatments on the changes from baseline.

Table 7			
Annualized event rate in higher-dose arm	Relative risk reduction	No. of events	Power
2%	25%	436	86%
	20%	449	66%
	15%	461	42%
2.5%	25%	544	92%
	20%	559	76%
	15%	575	50%
3%	25%	651	96%
	20%	669	83%
	15%	688	58%

III.F.7. Prior Treatment Effect

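### SAP 7.7 gives one direction (1 best, 5 worst) for all patient-reported scales, but protocol Table 5 codes two, possibly three, of the seven SAP domains the other way, and no recode is stated

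*SAP*

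**What the plan says.** SAP 7.7 lists seven patient-reported domains: Current Health, Physical function, Depression, Fatigue, Sleep disturbance, Social roles and activities, and Pain Interference. It then gives a single key for all of them: "Quality of life and functional status data are collected on numerical scales (1:excellent health-5:worst health". The scores are to be treated as continuous in mixed models. Because non-normality is expected, log and other transformations, distributions and link functions are left open.

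Protocol III.E.4.f also describes collection: "we will collect data on quality of life and functional status as shown in" Table 5. That table does not have one direction:

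- General Health and Quality of life: "5=Excellent; 4=Very good; 3=Good; 2=Fair; 1=Poor"
- Physical Function: "5=Without any difficulty; 4=With a little difficulty; 3=With some difficulty; 2=With much difficulty; 1=Unable to do"
- Social Roles & Activities, an item asking about trouble with leisure activities: "5=Never; 4=Rarely; 3=Sometimes; 2=Usually; 1=Always"
- Depression: "1=Never; 2=Rarely; 3=Sometimes; 4=Often; 5=Always"
- Fatigue and Sleep Disturbance: 1 is the answer for no problem and 5 the most severe.

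On analysis, protocol III.F.6 says only: "Variables collected on numerical scales will be analyzed as continuous variables". Neither that section nor SAP 7.7 or 7.9.3 mentions reversing any item.

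**The concern.** Both documents describe how the answers are collected, so for any item that Table 5 codes with 5 as best, the two statements cannot both be true. An analyst who applies the SAP key to data stored as in Table 5 would read a higher physical-function score as worse function, and would report the dose effect on that domain in the wrong direction. Social roles would be reversed in the same way, because never having trouble scores 5.

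The error would be hard to notice. With a linear model on the raw score, reversal leaves the size of the effect, its standard error and the p-value as they were. Only the sign, and so the clinical reading, is wrong.

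The lists of items also differ. Current Health and Pain Interference are not row names in Table 5 as available, and the overall Quality of life item is not on the SAP list. A reader cannot tell which item some of the SAP domains refer to.

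**Working it through.** The plan gives no figure to reproduce. The check compares directions domain by domain and then asks what a missed reversal does.

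**Step 1. Directions side by side.** The SAP key is 1 = best for every domain.

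| SAP 7.7 domain | Table 5 row | Best code in Table 5 | Against SAP key |
|---|---|---|---|
| Physical function | Physical Function | 5 | opposite |
| Social roles and activities | Social Roles & Activities | 5 | opposite |
| Current Health | none by name; General Health or Quality of life are candidates | 5 for either | opposite if matched |
| Depression | Depression | 1 | same |
| Fatigue | Fatigue | 1 | same |
| Sleep disturbance | Sleep Disturbance | 1 | same |
| Pain Interference | none in the text available | not given | cannot be compared |

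**Step 2. Count.**

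- Opposite by matched name: 2/7 = 29%.
- Opposite if Current Health is either overall item: 3/7 = 43%. The choice between the two items does not matter, since both have 5 as best.
- Same direction: 3/7.
- No Table 5 coding: 1/7.

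Within Table 5's own seven rows, four have 5 as best. That is a different list, because it includes the overall Quality of life item.

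**Step 3. Effect of a missed reversal, untransformed linear model.** Reversal replaces a score s by 6 − s. The intercept b0 becomes 6 − b0, every other fixed-effect coefficient changes sign, and the variance components and standard errors stay as they were. The two versions correlate −1.00. The absolute effect and two-sided p-value change by zero, and the sign is reversed.

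**Step 4. Effect if a log transform is used.** Take the five codes with equal weight (an assumption, for illustration).

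- ln(s) for s = 1 to 5: 0, 0.693, 1.099, 1.386, 1.609; mean 0.958.
- Deviations: −0.958, −0.264, 0.141, 0.429, 0.652. Sum of squares: 1.616.
- Cross-products of ln(s) with ln(6 − s): 2(−0.958)(0.652) + 2(−0.264)(0.429) + 0.141² ≈ −1.455.
- Correlation: −1.455/1.616 = −0.90.

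Because this is not −1.00, the direction chosen before taking logs affects more than the sign. A made-up two-arm example with 2,000 scores per arm shows the same. Reversal moved the t statistic from 4.34 to −4.34 on the raw scale, but from 4.61 to −3.90 after logs. These figures show that direction has to be settled before a transform. They do not estimate any error in this trial.

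**The case against.** The strongest reply is that this shows a mismatch of wording, not an analysis error. The table shells named in SAP 8 and the portal codebook are not among the documents available, and either may give the direction. An analyst would also see answer labels such as those for Physical Function and might not follow a short parenthetical against them. That stands as a limit on what can be concluded. It does not reconcile the two texts.

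Second, Table 5 may be the document that is out of date. It is a forward-looking statement, the SAP is a later document, and the different list of domains would fit a fielded instrument that had changed. This also stands: if the answers are stored with 1 as best, the SAP key is right and Table 5 needs correcting. SAP 1 does announce differences from the protocol, but only in statistical methodology, and how an answer was coded at collection is not methodology.

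Third, Pain Interference may be missing from Table 5 only because a row was lost when the text was read from PDF, and Current Health may simply be another label for General Health. Both are possible, so neither is counted here as a proven conflict.

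Fourth, with no summed score stated, separate models per domain do not strictly need a common direction, and the transform is only an option. That is fair. Stating the direction of each item would be enough, provided it is done before a transform is chosen.

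**Conclusion.** The conflict is real as written. SAP 7.7 states one direction for all the scales as collected, and protocol Table 5 contradicts it for two of the seven SAP domains by name, and for three if Current Health is one of the overall items. No reversal is stated in either document.

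The possible consequence is a reversed sign on those two to three secondary domains. In an untransformed linear model there is no change in absolute effect or p-value. With a nonlinear transform the estimates and p-values would also depend on the coding direction.

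This is minor in reach. The primary effectiveness and safety analyses are untouched, and no composite score is stated in which opposite directions could cancel. Confidence is high that the texts disagree. Whether any result would actually be reversed depends on the stored codes, which the documents do not show.

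**What to change.** 1. Check the stored codes of each item against the portal codebook and the call-center form, and correct whichever of the SAP key or Table 5 is wrong.
2. Replace the parenthetical in SAP 7.7 with a short table giving, for each item, its wording, stored codes and which end is favourable. If the table shells already give this, cite them in 7.7.
3. Fix the direction of each item before any transformation or link function is chosen. If one common direction is preferred for reporting, apply 6 minus the score only to the items stored the other way.
4. Reconcile the lists under "Quality of life and functional status components include" with Table 5: say whether Current Health is the General Health item, whether the overall Quality of life item is analysed, and which item and codes Pain Interference uses.

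The cost is a codebook check, some SAP wording and at most one line of recoding. No new data and no change of model are needed.
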